8.7 Safety analyses

Safety and toxicities of the study drug will be examined by documenting the type and grade of each adverse event (as defined by CTCAE v5, at baseline, and each follow-up visit). These data will be summarized with counts and percentages. In addition, each grade 3 or 4 adverse event will be described separately, and the plausibility of its causation by the study drug combination will be discussed.

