Interim analyses of the PERSIST-2 study led to Full Clinical Hold due to interim OS results in which the pooled pacritinib treatment arms (QD + BID) were compared with BAT and concerns about fatal intracranial hemorrhage, cardiac failure, and cardiac arrest. Updated analyses based on the locked database demonstrated that the QD dosing arm had a survival decrement compared to BAT (hazard ratio [HR]=1.18; p=0.6615), but the BID dosing arm had a trend for survival benefit (HR=0.68; p=0.3458).

In general, the safety observed in PERSIST-2 was similar to that observed in PERSIST-1, although differences were seen between the QD and BID pacritinib dosing arms. Except for hemorrhage, BID dosing generally was associated with lower rates of adverse events (AEs), including grade 3/4 and fatal events. The pacritinib BID arm had greater apparent efficacy for both SVR and reduction in TSS than either pacritinib dosed at 400 mg QD or BAT. Based on these efficacy data, the dose of 200 mg BID has been selected as the upper-level dosage regimen for the current dose-ranging study.

Most relevant to the current study, the safety impacts of prior JAK2 inhibitor treatment in PERSIST-2 were compared to patients who did not have such prior treatment. Incidences of treatment-emergent AEs (TEAEs) overall followed a similar pattern in the prior JAK2 inhibitor treatment and no prior JAK2 inhibitor treatment subgroups in the pacritinib and BAT treatment arms (pacritinib, 98.1% and 96.3%, respectively; BAT, 90.4% and 87.0%, respectively), with a comparable incidence in the QD and BID dosing arms. While thrombocytopenia showed similar rates between subgroups, anemia was increased in the no prior treatment group (pacritinib, 15.5% [13.5% QD and 17.6% BID] and BAT, 11.5% in the prior treatment group, and pacritinib, 35.5% [42.3% QD and 29.1% BID] and BAT, 19.6% in the no prior treatment group). Diarrhea, nausea, and vomiting had increases in incidence in the prior treatment group compared to the no prior treatment group.

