6.1.2 Serious Adverse Event (SAE)

Serious Adverse Event (SAE) means any untoward medical occurrence that results in any of the following outcomes:

- **Death.** Results in death.
- **Life-threatening.** Is life-threatening (refers to an AE in which the patient was at risk of death at the time of the event. It does not refer to an event which hypothetically might have caused death if it were more severe).

- **Hospitalization.** Requires inpatient hospitalization or prolongation of an existing hospitalization.
- **Disability/incapacity.** Results in persistent or significant disability or incapacity. (Disability is defined as a substantial disruption of a person's ability to conduct normal life functions).
- **Pregnancy**
- **Medically important event.** This refers to an AE that may not result in death, be immediately life-threatening, or require hospitalization, but may be considered serious when based on appropriate medical judgment, may jeopardize the patient, require medical or surgical intervention to prevent one of the outcomes listed above, or involves suspected transmission via a medicinal product of an infectious agent. Examples of such medical events include allergic bronchospasm requiring intensive treatment in an emergency room or at home, blood dyscrasias or convulsions that do not result in inpatient hospitalization, or the development of drug dependency or drug abuse; any organism, virus, or infectious particle (e.g., prion protein transmitting Transmissible Spongiform Encephalopathy), pathogenic or nonpathogenic, is considered an infectious agent.

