6.2 Collection and Reporting Requirements for Adverse Events and Serious Adverse Events

6.2.1 Collection of Adverse Events

All (or specify if only certain grade AE needed) adverse events (including SAEs) must be recorded in OnCore® and/or an adverse event log. All AEs required to be collected must be graded according to the CTCAE v5. When possible, signs and symptoms indicating a common underlying pathology should be noted as one comprehensive event. The investigator's or treating physician's assessment of AE attributions must also be documented.

AEs will be collected from the time the subject signs the consent form through 30 days post last dose of study drug(s). AEs will be tracked and followed until resolution, subject withdraws consent, or is lost to follow-up (including subjects who discontinue early). All adverse events collected per the protocol will be followed with appropriate medical management until they are resolved, if they are related to the study treatment, or until the investigator deems the event to be chronic.

Please see section 6.2.2 and table 6 to identify the adverse events that need to be reported.

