6.2.2 Reporting of Adverse Events and Serious Adverse Events

Please refer to table 6 below to identify adverse events that meet reporting requirements.

All serious adverse events (SAEs) that occur after the subject has signed the consent form through 30 days post last dose of study drug(s) will be reported. All SAEs will be followed until satisfactory resolution, or until the investigator deems the event to be chronic.

All serious adverse events (SAEs) must also be documented in OnCore®. SAEs (regardless of attribution) will be reported to CTI within 24 hours after the lead investigator learns of the event.

Attribution	SAE				AE		
	Grade 1, 2 & 3		Grade 4 and 5		Grade 3	Grade 4	
	Expected	Unexpected	Expected	Unexpected	Unexpected	Expected	Unexpected

Unrelated Unlikely	IRB ¹ and DSMC ² - Routine Review ³	IRB ¹ and DSMC ² - Routine Review ³	IRB ¹ - Routine Review ³ DSMC ² - Within 5 calendar days	IRB ¹ - Routine Review ³ DSMC ² - Within 5 calendar days	DSMC ² - Routine Review ³	DSMC ² - Within 5 calendar days	DSMC ² - Within 5 calendar days
Possible Probable Definite	IRB ¹ and DSMC ² - Routine Review ³ CTI Biopharma	IRB ¹ and DSMC ² - Within 5 calendar days FDA ⁴ CTI Biopharma	IRB ¹ - Routine Review ³ DSMC ² - Within 5 calendar days CTI Biopharma	IRB ¹ and DSMC ² - Within 5 calendar days FDA ⁴ CTI Biopharma	DSMC ² - Routine Review ³	DSMC ² - Within 5 calendar days	DSMC ² - Within 5 calendar days

Table 6

1. Guidance on adverse event reporting to the IRB is available online at MCW IRB Policies and Procedures.
2. For expedited DSMC reporting, the study coordinator/research nurse must notify the DSMC via email including the subject ID, date of event, grade, relatedness, expectedness, and a short narrative. The DSMC will review data entered into OnCore®.
3. For routine reporting, the events will be reported to IRB as part of the annual continuing progress report and the DSMC will review data entered into OnCore® at the time of scheduled monitoring.
4. Fatal or life-threatening SAEs meeting the criteria indicated in the above table will be reported to FDA no later than seven calendar days after study staff's initial awareness of the event. If the SAE is not fatal or life-threatening and meets the above criteria, the timeline for submitting an IND safety report to FDA is no later than 15 calendar days after study staff's initial awareness of the event. See section 6.2.3 for detailed reporting instructions.

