Bleeding: Pacritinib may increase the risk of bleeding. Reports of serious bleeding events, including life-threatening and fatal events, have been reported. These bleeding events were generally without lasting sequelae, although life-threatening and fatal events of hemorrhage, including intracranial hemorrhage, were observed more frequently in pacritinib-treated patients compared with BAT patients. Risk factors for bleeding with pacritinib may include prior bleeding events and anti-platelet and anti-coagulant medications in addition to severe thrombocytopenia. Concomitant use of drugs affecting hemostasis, such as aspirin and other antiplatelet agents, other anticoagulants, heparin, and thrombolytic agents, may increase the risk of bleeding. Refer to the protocol for guidance on dose modifications for pacritinib-related bleeding events.

Cardiac: QTc prolongation has been observed in patients treated with pacritinib. Prior to initiating treatment with pacritinib, patients should undergo an ECG to establish baseline QTc and an echocardiogram (or other appropriate methodology) to establish baseline left ventricular ejection fraction; patients should be monitored periodically for changes in their QTc. Pacritinib should not be used in patients with uncontrolled cardiac dysrhythmias, QTc prolongation >450 ms, or other factors that increase the risk for QT prolongation (e.g., heart failure, hypokalemia, hypomagnesemia, or a history of long QT interval syndrome). Caution should be used when co-administering other medicinal products with the potential to elongate QT interval. Ejection fraction should be monitored at baseline, after one month on treatment, after three and six months on treatment, and every six months thereafter; pacritinib dose should be modified if significantly reduced ejection fraction is detected. Additional ECG and ejection fraction assessments should be performed as clinically indicated. Refer to the protocol for guidance on dose modifications for pacritinib-related QTc prolongation.

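### Section 8.7 gives an individual description and causality discussion to grade 3 or 4 adverse events only, so a fatal (grade 5) event is left out of that part of the final safety analysis

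*Combined protocol and SAP*

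**What the plan says.** Section 8.7 has two layers. The first covers every adverse event under CTCAE version 5: safety is examined by "documenting the type and grade of each adverse event", and "These data will be summarized with counts and percentages". There is no upper grade limit, so a grade 5 event is included. The second layer is the only interpretive step: "each grade 3 or 4 adverse event will be described separately, and the plausibility of its causation by the study drug combination will be discussed". It names grades 3 and 4 only.

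Other sections handle deaths explicitly:

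- Section 6.1.2 makes an event serious if it "Results in death".
- Section 6.2.1 says the investigator's or treating physician's "assessment of AE attributions must also be documented", with no grade ceiling.
- Table 6 in Section 6.2.2 puts grade 5 serious events in the same columns as grade 4. Every one goes to the DSMC within five calendar days, whatever its attribution or expectedness. For such notices, "the study coordinator/research nurse must notify the DSMC via email including the subject ID, date of event, grade, relatedness, expectedness, and a short narrative".

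On the drug's history, Section 7.7 states that "life-threatening and fatal events of hemorrhage, including intracranial hemorrhage, were observed more frequently in pacritinib-treated patients compared with BAT patients". Section 1.5.4 says the PERSIST-2 clinical hold arose from interim survival results and "concerns about fatal intracranial hemorrhage, cardiac failure, and cardiac arrest". The same section reports an imbalance in fatal and life-threatening events in PERSIST-1.

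**The concern.** The individual review stops one grade short of the worst outcome. Followed as written, the final safety analysis would discuss whether a grade 3 fatigue was caused by the drug, but would not be required to do so for a fatal intracranial bleed.

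Safety is a secondary endpoint (Section 2.5). The trial has one arm, so there is no concurrent rate of death against which an excess could be seen. Whether a death counts against the drug therefore depends on case-by-case assessment, which is what this sentence is meant to provide.

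**Working it through.** The main check is textual. Section 8.7 contains no figure to reproduce.

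**Step 1. Could grade 3 or 4 be loose wording that takes in deaths?** The protocol's own usage says not:

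| Place | How fatal events are handled |
|---|---|
| Section 1.5.4, PERSIST-2 | Fatal events are listed alongside grade 3/4 events as a further category, and fatal rates are given apart from grade 3/4 rates |
| Section 1.5.4, PAC203 | Seven patients are counted with grade 3 or 4 hemorrhage; two fatal bleeds are then given separately as grade 5 |
| Section 6.2.2, Table 6 | Where deaths are meant to be covered, the column heading names grade 5 together with grade 4 |
| Appendix 7 (diarrhea grading) | Grade 5 is death |

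The document keeps grade 3/4 and grade 5 apart and names grade 5 when it intends to include it.

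**Step 2. Does any other part of Section 8 supply the missing review?** Section 8.5 covers PSA, time-to-event and testosterone endpoints. Section 8.8 covers baseline characteristics and a listing of each subject's disposition. Section 8.10 covers missing data. None asks for a description or causality discussion of a death.

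**Step 3. What happens to one fatal event under the plan as written?**

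| Step | Grade 3 or 4 event | Grade 5 event |
|---|---|---|
| Graded and recorded (6.2.1) | Yes | Yes |
| Attribution documented (6.2.1) | Yes | Yes |
| In counts and percentages (8.7) | Yes | Yes |
| DSMC notice with a brief account (Table 6) | Every grade 4 event; some serious grade 3 events | Yes, every cell |
| Own description and causality discussion in the final analysis (8.7) | Yes | **Not required** |

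The gap is confined to the last row.

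**Step 4. How likely is the gap to matter?** This is context only. The documents give no fatal-event rate for men with biochemical relapse, so the risk *p* per man is an assumption. With *n* men and independent outcomes, the chance of at least one fatal event is 1 − (1 − *p*)^*n*.

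| Assumed *p* | *n* = 10 (interim cohort) | *n* = 46 (full study) |
|---|---|---|
| 0.5% | 1 − 0.995^10 = 4.9% | 1 − 0.995^46 = 20.6% |
| 1% | 1 − 0.99^10 = 9.6% | 1 − 0.99^46 = 37.0% |
| 2% | 1 − 0.98^10 = 18.3% | 1 − 0.98^46 = 60.5% |

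These are chances that a death occurs, not that it goes undescribed. They show only that the case is not remote at full enrollment.

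**The case against.** The strongest reply is that deaths are well covered already. They are serious by definition, attribution is recorded at every grade, and each grade 5 serious event goes to the DSMC within days with relatedness and an account. Section 6.2 also sends all serious events to the drug supplier within 24 hours, and fatal events that are related and unexpected to the FDA within seven days. Section 8.7 itself counts them, and the restricted sentence is an addition to that count. No competent report would pass over a death in silence.

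Most of this stands, and it limits the point. A reader might infer that fatal events escape the safety analysis, or all written review. The documents do not support that, for the reasons just given. What the reply does not do is change Section 8.7. The Section 6.2 rules serve oversight while the trial runs; they do not say what the final analysis must contain.

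Three other inferences are tempting and should be resisted:

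- **That fatal events are the protocol's leading concern.** Section 7.7 also sets out gastrointestinal, platelet and cardiac risks, and does not rank them.
- **That events are counted again at each visit.** Section 8.7 mentions documentation at baseline and follow-up visits but does not say that counts are summed across visits. Section 6.2.1 points to event-level records followed to resolution. The counting unit is unstated, which is not the same as wrong.
- **That the PAC203 death rate applies here.** The 10 deaths on treatment or within 30 days (10/161 = 6.2%) were in myelofibrosis patients pooled over three dose groups, and the causes included disease progression. The present trial requires platelets of at least 100,000 and excludes recent significant bleeding, anticoagulants and NYHA class II or worse heart failure. That rate is not a usable upper bound for these men.

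**Conclusion.** The point holds in a narrow form and is minor. As worded, Section 8.7 leaves a grade 5 event outside the individual description and causality discussion in the final safety analysis, although the event is graded, tabulated, attributed and reported to the DSMC. The conclusion rests on the plain wording of Section 8.7, on the protocol's consistent separation of grade 5 from grade 3/4, and on the absence of any other provision in Section 8. It does not depend on the assumed event rates.

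No type I error, power, sample size or efficacy result is affected. The sentence is worth correcting because the omitted grade is the one for which this drug has a documented history, and because attribution in a single-arm trial depends on individual review.

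**What to change.** Reword the last sentence of Section 8.7 to this effect: *Every adverse event of grade 3 or higher, including each death (grade 5), is given its own description, with a discussion of whether pacritinib plausibly caused it.*

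Naming pacritinib also removes the reference to a drug combination, which looks like leftover wording in a single-agent trial and has no analytic consequence.

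The cost is one sentence. Grade, attribution and a short account of each fatal serious event are already collected under Section 6.2, so no new data, visits or forms are needed, and nothing else in Section 8 changes.

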8.8 Other analyses

Demographic and clinical characteristics of the patient population will be reported using appropriate descriptive statistics such as frequencies and percentages with standard errors for categorical variables, mean with standard error or median with quartiles for continuous variables. The disposition of each subject will be reported as a listing.

8.9 Interim analyses

An interim analysis for futility will be performed when 10 patients have been treated and followed for six months. The Kaplan-Meier estimate of the six-month PSA-progression-free survival using the data from the first 10 subjects and any subject who have been enrolled during the six-month follow-up period of the tenth subject will be computed and compared to 66% using a z-test at a one-sided 10% significance level. The study will be stopped for futility if the hypothesis is rejected for the alternative of the 6-month PSA-progression-free survival being lower than 66%.

8.10 Missing data

For all outcomes, summary statistics will include the count of missing and non-missing values. Patients with missing value for the primary outcome, PFS, will be censored at the time when last known to be alive and without progression. A similar approach will be used for other time-to-event outcomes, such as time to PSA nadir. Secondary outcomes requiring numeric values, such as geriatric assessments, PSA and testosterone levels will be analyzed among patients with non-missing values as required for each analysis (e.g., non-missing value at specific time point for cross-sectional analysis, and non-missing values at two time points for change analyses). The limitations of extensive missingness, if present, will be clearly noted in all reports and any related findings will be interpreted with caution.

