3 STUDY DESIGN

3.1 General Description

This is a single-arm, open-label phase 2 study to evaluate the role of pacritinib for patients with biochemical relapse after definitive treatment for prostate cancer. Patients will receive pacritinib 200 mg twice daily. To be eligible, patients are not allowed to have been treated with a JAK2

inhibitor. Assigned treatment will continue until the patient experiences progressive disease or intolerable adverse events (AEs), withdraws consent, initiates new PC-directed therapy, or the study is terminated. In addition to the above, patients will be considered to have discontinued treatment if pacritinib is held for >28 consecutive days due to treatment toxicity, or if treatment is discontinued for lack of efficacy, or at the request of the principal investigator or the patient. This study will be monitored by an Independent Data Monitoring Committee (IDMC).

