4.6 Discontinuation of Study Treatment, Withdrawal, and Compliance

Treatment duration is 2 years. Patients may continue drug beyond two years if, in the opinion of the treating physician, the patient is benefitting from treatment and benefits outweigh any risks of therapy

Discontinuation from the study treatment does not mean discontinuation from the study. The subject will be considered in follow-up, study procedures should still be completed as indicated by the study protocol, and AEs/SAEs will continue to be reported according to this protocol.

In the absence of treatment delays due to adverse events, study treatment/intervention may continue until:

- Disease progression per PCWG3 guidelines
- General or specific changes in the subject's condition renders the subject unacceptable for further treatment in the investigator's judgment.
- An inter-current illness that prevents further treatment administration.
- The subject decides to withdraw from the study.
- The subject has significant noncompliance with the protocol (see below).
- Unacceptable adverse event(s) and/or dose level reduction beyond requirements as detailed in this protocol.
- The clinical need for concomitant therapy that is not permitted in the study.
- Subjects who sign the informed consent form, enroll and receive the study intervention, but subsequently withdraw, or are withdrawn or discontinued from the study will not be replaced.

Progression of disease

Progression of disease per PCWG3 is defined as one or more of the following:

PSA progression

Recognize that a favorable effect on PSA may be delayed for \geq 12 weeks, even for a cytotoxic drug. Monitor PSA by cycle but plan to continue through early rises for a minimum of 12 weeks unless other evidence of progression.

If there is a decline in PSA from baseline: record time from baseline to the first PSA increase that is $\geq 25\%$ and ≥ 2 ng/mL above the nadir, and which is confirmed by a second value ≥ 3 weeks later (i.e., a confirmed rising trend).

If there is no decline in PSA from baseline but stable PSA at 12 weeks: PSA progression will be defined as $\geq 25\%$ and ≥ 2 ng/mL from PSA at 12 weeks .

Radiographic progression

Radiographic progression will be assessed per RECIST 1.1. Any new unequivocal bone lesion is considered progression, except if that lesion appears in the first post-treatment scan; in that

case, document the event, continue treatment until two additional new lesions appear, and record both events.

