8.3 Study design and sample size

A two-stage single-arm design based on the methods of Huang et al (2010) will be used.

The design is based on a modification of a binomial two-stage design that allows the incorporation of data from subjects with less than six months of follow-up at the interim analysis. The study will enroll up to 46 subjects with an interim analysis performed when 10 patients have been treated and followed for 6 months. The underlying binomial design would stop for futility if there are four or fewer patients alive without PSA progression at six months among these 10 patients. The modified futility decision will use the Kaplan-Meier estimate of the six-month PSA-progression-free survival using the data from the first 10 subjects and any subject who have been enrolled during the six-month follow-up period of the tenth subject. If the six-month PSA-progression-free survival is significantly lower at a one-sided 10% significance level than the clinically meaningful value of 66% defined by the alternative hypothesis, the study will be stopped for futility. If no new patients would be enrolled during the follow-up period, this decision rule is equivalent to the one defined by the binomial design.

If the study is not stopped for futility, study enrollment continues until 46 subjects are enrolled. The final analysis will be performed when all subjects have been followed for at least six months. The null hypothesis will be rejected, and the study drug will be considered promising if 27 or more patients are alive without PSA progression at six months among the 46 patients. The underlying binomial design yields a type I error rate of 10% if the underlying six-month PSA-progression-free probability is 50% (and the median PSA-progression-free survival is 6 months), and power of 80% when the six-month PSA-progression-free probability is 66%, which corresponds to a median of 10 months if the time to PSA progression is exponentially distributed. Simulation studies confirmed that the design with the modified futility stopping method maintains these properties. If the median PSA-progression-free survival is six months, then the binomial design would stop at the interim analysis with 38% probability. Assuming an enrollment rate of 1.5 subjects/month, the modified futility stopping rule increases this probability of stopping at the interim analysis to 45%.

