8.4 Analysis of primary endpoint

The probability of PSA-progression-free survival over time will be estimated using the Kaplan-Meier method and shown with 80% pointwise confidence limits. The six-month PSA-progression-free survival will be compared to the null-value of 50% using a z-test at a one-sided 10% significance level.

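### As written, a PSA taken after the start of new prostate-cancer therapy can serve as evidence of six-month PSA-progression-free survival on pacritinib

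*Combined protocol and SAP*

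**What the plan says.** The primary endpoint (2.4) is six-month PSA-progression-free survival, so the only events are death and PSA progression. It is used in three places.

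- **8.3, final count.** The null is rejected if 27 or more men are "alive without PSA progression at six months among the 46 patients".
- **8.4, primary analysis.** The Kaplan-Meier estimate at six months "will be compared to the null-value of 50% using a z-test", one-sided at 10%.
- **8.9, futility look.** The same estimate "will be computed and compared to 66% using a z-test at a one-sided 10% significance level".

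The one censoring rule is in 8.10: "Patients with missing value for the primary outcome, PFS, will be censored at the time when last known to be alive and without progression". It is a rule for missing values.

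New therapy appears elsewhere, but never as part of the endpoint. In 3.1, treatment ends when a man "initiates new PC-directed therapy, or the study is terminated", and a man is also off treatment if pacritinib is held too long for toxicity "or if treatment is discontinued for lack of efficacy". Section 4.6 adds: "Discontinuation from the study treatment does not mean discontinuation from the study". Such a man stays in follow-up with study procedures. The 4.6 definition of PSA progression does not exclude PSA values taken under another drug. Time to the next antineoplastic therapy is a separate secondary endpoint (2.5).

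**The concern.** The plan itself makes switching before progression foreseeable. Treatment may stop for toxicity, lack of efficacy or patient choice. Section 1.1 names intermittent androgen deprivation as the standard of care for these men, and those who stop remain under observation. After a PSA decline, 4.6 requires a rise to be confirmed at least three weeks later, so androgen deprivation started after a first rise can prevent the confirming value.

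Consider a man who starts androgen deprivation at month 4 without confirmed progression and has a suppressed PSA later. He is alive, has no recorded progression and has a PSA value, so 8.10 does not apply to him. Read literally, 8.3, 8.4 and 8.9 treat him as progression-free at six months because of a different drug.

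In a single-arm trial judged against a fixed 50%, that raises the estimate with nothing to offset it. Leaving the point open also allows the choice to be made after the data are seen, in a trial where one man can decide a 27-of-46 result.

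**Working it through.** **1. The plan's own figures.**
- An exponential time with 66% free at six months has median 6 × ln 2 / (−ln 0.66) = 10.0 months, as stated.
- P(4 or fewer of 10 | 50%) = 37.7%, matching the stated 38%.
- The modified futility rule, simulated under the plan's accrual ("Assuming an enrollment rate of 1.5 subjects/month"), stops with probability 45.1% at the null, against the stated 45%.
- The exact count rule is the sum over x = 5 to 10 of Bin(x; 10, p) × P[Bin(36, p) ≥ 27 − x]. It gives 13.3% at p = 0.50 and 83.1% at p = 0.66, not the stated 10% and 80%. That mismatch is a separate matter, but it sets the starting level of the count figures below.

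**2. Model for switching (assumed).** A share s of men would switch by month 6, independently of PSA, with s = 5%, 10% or 15%. The switch hazard is b = −ln(1 − s)/6 and the progression hazard is a = −ln(p0)/6. The probability of switching first, before month 6, is w = b/(a + b) × [1 − exp(−6(a + b))].

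At p0 = 0.50, w = 0.036 / 0.073 / 0.109, or 1.7 / 3.3 / 5.0 of 46 men. Of these, 46 × (w − 0.5s) = 0.5 / 1.0 / 1.6 would have progressed by month 6.

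**3. Literal reading of the count.** If every switcher has a later suppressed PSA, the apparent rate is p = 0.5(1 − s) + w = 0.511 / 0.523 / 0.534. The exact false-positive risk rises from 13.3% to 16.7 / 20.7 / 25.4%.

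**4. Literal reading with limited PSA timing (simulated).** As far as the damaged calendar can be read, a man whose last dose is at month t has a PSA at about t + 1 (30-day visit) and then about t + 7 (six-monthly follow-up). The simulation takes the switch date as the last-dose date. Only PSA values available at each analysis count, and every later PSA is suppressed. At a true rate of 50%:

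| Quantity | No switching | 5% | 10% | 15% |
|---|---|---|---|---|
| 8.4 z-test, false positive | 8.4% | 10.8% | 13.5% | 17.1% |
| 27-of-46 count, false positive | 13.2% | 15.5% | 17.6% | 20.3% |
| Futility stop | 45.1% | 42.6% | 40.6% | 38.3% |

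**5. Alternative handlings, switching independent of PSA (5 / 10 / 15%).**
- Censor at the last PSA before the switch, 8.4 z-test: false positive about 9.5%, power about 78 / 77 / 76% (78% with no switching).
- Count the switch as an event, 8.4 z-test: false positive 4.3 / 1.9 / 0.7%, power 62 / 44 / 28%.
- Count the switch as a failure in the 27-of-46 rule, p = p0(1 − s): exact false positive 7.4 / 3.8 / 1.7%, power 70.6 / 54.7 / 37.8%, against 83.1% with no switching.

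The power figures assume that 66% refers to PSA progression and death alone.

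**6. Switching prompted by PSA (assumed).** Suppose half the switchers change within the two months before a progression due by month 6. The z-test false-positive risk is then:

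| Switching | Literal | Censored | Event |
|---|---|---|---|
| 5% | 16.4% | 13.1% | 5.9% |
| 10% | 28.5% | 18.2% | 4.3% |

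**7. A concrete result.** Take 24 men truly progression-free and three men with PSA suppressed by new therapy.
- Counted literally: 27 of 46, which meets 8.3 (z = 1.20, short of the 1.28 that 8.4 needs; a fourth such man gives 28 of 46 and z = 1.51).
- Counted as failures: 24 of 46 = 52.2%.
- Censored early: about 24 of 43 = 55.8%, z = 0.77.

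Only the literal count gives a success under 8.3.

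**The case against.** The strongest objections concern size and likelihood.

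- **The inputs are assumed.** The switch rates, the independence and the PSA-driven pattern are not in the documents. The t + 1 and t + 7 timing comes from a broken table. This stands: the figures illustrate and do not estimate.
- **The effect on the primary test can be modest.** At 5% independent switching the z-test runs at 10.8% against a nominal 10%, and the futility effect is small. This also stands. The count figures look worse partly because they start from 13.3%.
- **Early switching is discouraged.** Sections 4.6 and 5.1.2 envisage at least 12 weeks of treatment despite early PSA rises. Appendix 6 lists leuprolide and degarelix as prohibited; 5.3 applies this to the treatment phase and 7.6 throughout the study. This makes switching less common, but 3.1 still anticipates new therapy, and none of it gives such a man an endpoint status.
- **The text hints at excluding such values.** Section 2.2 describes the nadir as the lowest PSA on treatment, and the summary ties progression to PCWG3. An analyst might infer from the first that PSA under another drug is not used. It is only an inference, made for a secondary objective, and the progression rule written out in 4.6 is silent. What PCWG3 itself says cannot be checked from these documents.
- **Switchers will be visible.** Time to next therapy is analysed (8.5) and disposition is listed (8.8). Visibility helps a reader but does not fix the analysis in advance.

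**Conclusion.** The gap is real and should be fixed. Followed as written, the endpoint and its only censoring rule let a PSA taken after new therapy stand as evidence of freedom from progression, which biases the result towards pacritinib. Confidence is high on the silence of the documents and low on the size. On the assumed 5 / 10 / 15% scale the 8.4 false-positive risk goes from about 8.4% to about 11 / 13 / 17%, and higher if a rising PSA prompts the switch.

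Three stronger readings are not supported:

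- A reader might infer that every switcher becomes a success. A man who stops early may have no later PSA by the time of analysis and would then fall under 8.10.
- A reader might infer that the plan intends to credit another drug's effect. The documents do not say so, and an analyst could censor instead.
- A reader might infer that every switcher must be a failure in the 27-of-46 count. Nothing in the documents requires it, and exact power would fall from 83.1% to 70.6 / 54.7 / 37.8%.

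**What to change.** Change the analysis definitions only and leave the treatment-stopping rules as they are.

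1. In 8.3, 8.4, 8.9 and 8.10, state that PSA values taken after the start of any new antineoplastic therapy do not contribute to the primary endpoint.
2. In both the interim and final Kaplan-Meier analyses, extend the 8.10 rule: censor such a man at his last PSA before new therapy.
3. Add a sensitivity analysis that counts the start of new therapy as an event, and report how many men are affected.
4. In 8.3, say how the 27-of-46 count treats these men so that it agrees with 8.4. A censored man has no six-month status, so the count needs its own sentence, for example one saying whether 8.3 or 8.4 governs.

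No new data are needed, because the start date is already required for a secondary endpoint. The power cost is small: about 76% to 78% for the 8.4 test, against 78% with no switching. The remaining weakness is that censoring is not neutral when a rising PSA prompts the switch (about 13% false positive at 5% switching and 18% at 10%, in the scenario above). That is the reason for the event sensitivity analysis.
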